### **10.4 Patient Information and Consent**

Informed consent is obtained from the patient in writing before documentation of any data. In countries where required by law or regulation, the physician must have the IEC's written approval/favourable opinion of the written informed consent form and any other written information to be provided to patients prior to the start of the observation.

### **10.5 Patient Insurance**

In this study, data on routine treatment of patients in daily practice will be documented. Data will be analysed using epidemiological methods. Treatment including diagnosis and monitoring of therapy will exclusively follow routine daily practice. Current medical daily practice will be observed, and for the patient no risks beyond regular therapy exist, so that there is no additional hazard arising from study participation. As no study related risks

exist, there is no need to protect the patient additionally by a patient insurance. The general regulations of medical law and the professional indemnity insurance of the physicians and, respectively, the institutions involved provide sufficient protection for both patient and physician.

Furthermore, no study medication will be provided to participants. Thus, product insurance is covered by the existing product liability.

### **10.6 Confidentiality**

The MAH as well as all physicians participating in this study ensure adherence to applicable data privacy protection regulation. Data will only be transferred in an encoded form (pseudonymised form). The entire documentation made available to the MAH does not contain any data which, on its own account or in conjunction with other freely available data, can be used to re-identify natural persons. The physicians participating in this study are obligated to ensure that no documents contain such data.

All records identifying the patient will be kept confidential and will not be made publicly available. Patient names will not be supplied to the MAH. If a patient name appears on any document, it must be obliterated before a copy of the document is supplied to the MAH. Study findings stored on a computer will be stored in accordance with local data protection laws.

The physician will maintain a list to enable patient records to be identified in case of queries. In case of a report of an event (i.e., AEs, SAEs, ADRs, SADR, special situations), the responsible pharmacovigilance person may ask for additional clarification. In that case, the company is not allowed to directly contact the patient. All additional information will be provided by the physician.

# 11 Management and Reporting of Adverse Events/ Adverse Drug Reactions

## 11.1 Definitions

### AE

An AE is any untoward medical occurrence in a patient administered a medicinal product and which does not necessarily have to have a causal relationship with this treatment. An AE can therefore be any unfavourable and unintended sign (e.g., an abnormal laboratory finding), symptom, or disease temporally associated with the use of a medicinal product, whether or not considered related to this medicinal product [15].

The AE may be:

- A new illness
- Worsening of a sign or symptom of the condition under treatment or of a concomitant illness
- An unwanted effect of the study medication
- An unwanted effect of concomitant therapy
- Treatment exposure via mother (exposure during conception, pregnancy, childbirth, and breastfeeding)
- An effect related to lack of drug effect
- An effect related to drug interactions
- An effect related to medication errors
- An effect related to off-label use
- An effect related to overdose, drug abuse (use for nonclinical reasons) or drug misuse, drug dependency
- An effect related to pre-existing condition improved (unexpected therapeutic or clinical benefits are observed)
- Any combination of one or more of these factors

As mentioned above no causal relationship with a study medication is implied by the use of the term “AE”.

### ADR

An ADR is any AE suspected as being “at least possibly related” to Yselty®. It is defined as a response to a medicinal product which is noxious and unintended. The assessment of the causal relationship between an AE and the administration of treatment is a clinical decision based on all available information at the time of the completion of the eCRF. The

---

 Considered as special situations in this study. See definition at end of this section.

assessment is based on the question whether it is “at least possibly related” to Yselty® in accordance with WHO-Uppsala Monitoring Centre (UMC) Causality Categories (see Table 3). It is the reporting physician’s responsibility to evaluate whether an AE is related to Yselty® prior to reporting the AE to MAH.

**Table 3 WHO-UMC Causality Categories**

Causality term	Assessment criteria
Certain	
 
• Event or laboratory test abnormality, with plausible time relationship to drug intake
 
• Cannot be explained by disease or other drugs
 
• Response to withdrawal plausible (pharmacologically, pathologically)
 
• Event definitive pharmacologically or phenomenologically (i.e., an objective and specific medical disorder or a recognised pharmacological phenomenon)
 
• Rechallenge satisfactory, if necessary
 

Probable/Likely	
 
• Event or laboratory test abnormality, with reasonable time relationship to drug intake
 
• Unlikely to be attributed to disease or other drugs
 
• Response to withdrawal clinically reasonable
 
• Rechallenge not required
 

Possible	
 
• Event or laboratory test abnormality, with reasonable time relationship to drug intake
 
• Could also be explained by disease or other drugs
 
• Information on drug withdrawal may be lacking or unclear
 

Unlikely	
 
• Event or laboratory test abnormality, with a time to drug intake that makes a relationship improbable (but not impossible)
 
• Disease or other drugs provide plausible explanations
 

Unassessable	
 
• Report suggesting an adverse reaction
 
• Cannot be judged because information is insufficient or contradictory
 
• Data cannot be supplemented or verified
 

### **SAE/SADR**

An AE or ADR is serious if it:

- Results in death
- Is life-threatening
- Requires inpatient hospitalisation or prolongation of existing hospitalisation
- Results in persistent or significant disability or incapacity
- Is a congenital anomaly or birth defect
- Is medically important

Medical and scientific judgement should be exercised in deciding whether other situations should be considered serious, such as important medical events that might not be immediately life-threatening or result in death or hospitalisation but might jeopardise the patient or might require intervention to prevent one of the other outcomes listed in the definition above.

## **Special Situations**

For this study, special situations are reports of the use of Yselty® with or without AE during pregnancy and/or breast feeding (see section 11.2), drug interactions, medication abuse, medication misuse, medication overdose, medication errors, unexpected therapeutic or clinical benefit from product use, lack of efficacy, off-label use, and occupational exposure.

Special situations may occur independently or in conjunction with an associated AE. Instances of special situations without an associated AE or special situation associated with a non-serious AE/ADR are required to be reported within 7 calendar days. Instances of special situations associated with a SAE or SADR, are required to be reported as per timelines for the SAE or SADR reporting i.e., within 24 hours of awareness.

### **11.2 Drug Exposure Before or During Pregnancy or Lactation**

If a pregnancy occurs during the study, although it is not an SAE itself, it must be documented and forwarded to the MAH within the same time limits as an SAE (see section 11.3) and the process below will be followed; all other data collection will cease.

Drug exposure before or during pregnancy, where the embryo or foetus may have been exposed to Yselty® (through maternal exposure), will be followed up in order to collect information on the outcome of the pregnancy and development of the child after birth.

For pregnancies, the following information will be collected: prior pregnancies (including outcome of pregnancy), expected date of delivery, prenatal tests, pregnancy outcome, information on the child (e.g., sex, height, weight), complications, and causal relationship to study drug Yselty® (if abnormal outcome).

Individual cases with an abnormal outcome associated with Yselty® following exposure before or during pregnancy will be collected as an SAE. This especially refers to:

- Reports of congenital anomalies or developmental delay, in the foetus or the child
- Reports of foetal death and spontaneous abortion
- Reports of AEs considered related to Yselty® (suspected ADRs) in the neonate that are classified as serious

Drug exposure during lactation is not considered an AE. However, events will be followed up in order to collect information on the drug effects during lactation and development of the child.

Additionally, data will be collected and utilised, as appropriate, from the RMP targeted follow-up questionnaire on exposure in pregnancy/pregnancy outcome.

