## 8 Research Question and Objectives

Data in patients taking Yselty® in the real-world setting and for more than 1 year is needed to better understand certain safety parameters associated with long-term use. The overall study aim is to assess the long-term safety of Yselty® when used in real life clinical practice.

The primary objective is:

- **I.** To evaluate routinely collected data on long-term safety (>12 months) in relation to BMD with use of Yselty® 200 mg (with ABT) and 100 mg (with and without ABT) dosing regimens.

The exploratory objectives are:

- **II.a** To evaluate the incidence of osteoporosis or fractures suspected to be due to osteoporosis
- **II.b** To evaluate liver enzyme levels above the upper limit of normal and correlated events collected as part of clinical practice
- **II.c** To evaluate any routinely collected clinical data on mood disorders
- **II.d** To evaluate the incidence of uterine endometrial and mammary gland adenocarcinoma
- **II.e** To describe treatment patterns for Yselty® dosing regimens with and without ABT
- **II.f** To evaluate patient adherence to Yselty® treatment
- **II.g** To evaluate any routinely collected clinical data on cardiac disorders indicative for QT interval prolongation
- **II.h** To assess if physicians who prescribe Yselty® follow the summary of product characteristics (SmPC) recommendations including performance of annual dual-energy X-ray absorptiometry (DXA) scans and adherence to the requirement of not prescribing the Yselty® 200 mg regimen without concomitant ABT
- **II.i** To evaluate the incidence of adverse drug reactions (ADRs), serious adverse drug reactions (SADRs) and pregnancies (including pregnancy follow-up)
- **II.j** To evaluate BMD change in patients with routinely collected DXA scans at multiple timepoints to assess mean change of BMD z- and t-scores from baseline or 12-month assessment during long-term (>12 months) use of Yselty®.

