#### **Follow-up visit(s) for patients who experienced BMD decrease or osteoporosis during the study**

Patients who discontinued treatment with Yselty® but had BMD decrease or osteoporosis during the study should be observed in the study for up to 24 months after the last administration of Yselty®. Documentation of further visits by the physician during the further follow-up period will be limited to BMD assessments and relevant concomitant medications. For AE reporting please see section 11.3.

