BMD will be displayed as absolute and relative change in density ( $\text{g}/\text{cm}^2$ ) and absolute value and relative change of z-scores and t-scores over time by means of summary statistics; e.g., DXA scans performed at baseline (if available) vs. timepoint 1 – 1st year (+/-6 months) after treatment initiation, timepoint 1 – 1st year (+/-6 months) after treatment initiation vs. DXA scans performed at timepoint 2 – 2nd year (+/-6 months), where the measurements are at least 6 months apart. This is continued in the same way for further years if the sample size is at least 5 patients. Changes are only analysed if e.g., the machine types, the location of the scan and other criteria that allow comparability are consistent. A subgroup analysis of t-scores for the subgroup of postmenopausal patients and of z-scores in the subgroup of premenopausal patients will be conducted, if sample size allows. Additionally, patients who experienced BMD decrease during the study but continued to be observed in the study, regardless of the reason for which Yselty® treatment was discontinued, will be investigated as a separate subgroup. This subgroup analysis will include the presentation of both absolute value and relative change of z-scores and t-scores after discontinuation. If the sample size permits, this subgroup will be stratified based on whether alternative treatments administered after discontinuation may also lead to a decrease in BMD (refer to “previous systemic treatments” in section 9.3.3).

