### **11.3 Documentation**

All AEs under exposure to Yselty® that have been reported by the patient to the physician (i.e., AEs, SAEs, ADRs, SADR, special situations) will be documented on the AE Report form in the eCRF/EDC system. Assessment on seriousness and relationship to product, treatment duration, action taken, and outcome of the event will be provided by the treating physician, who will also be responsible for following up on the outcome of SAEs, if this information is not available when first reported. Where required, physicians might be contacted directly, per the MAH's internal follow-up procedure, to obtain further information.

In addition, for selected events (see section 9.4), the MAH will utilise the targeted follow-up questionnaires, where applicable, as per the latest version of the RMP (see section 15.1). The purpose is the ongoing monitoring and safety evaluation of these events.

The documentation of any event within the eCRF ends with the completion of the follow-up of the patient or until it is no longer possible (e.g., lost to follow-up, death, withdrawal). In case of discontinuation of Yselty® for any reason, all events will be collected that occurred up to 30 days after the last administration. Since the  $t_{1/2}$  elimination time of linzagolix is 15 hours, exposure has well ended after 30 days. However, patients who discontinued treatment with Yselty® but experienced BMD decrease or osteoporosis during the study will continue to be followed up unless they have completely withdrawn from the study, and all AEs associated with BMD loss (e.g., osteoporosis, osteopenia, fractures) and all ADRs will be collected irrespective of treatment discontinuation.

All AEs will be summarised in tabulated forms in the interim safety analysis and final study report.

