### **Special situations**

Special situations of drug interactions, medication abuse, medication misuse, medication overdose, medication errors, unexpected therapeutic or clinical benefit from product use, lack of efficacy, off-label use, and occupational exposure must be documented and forwarded to the MAH within 7 calendar days. Drug exposure during pregnancy or lactation must be documented and forwarded to the MAH by the physician immediately (within 24 hours of awareness) (see section 11.2).

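### Section 11.2 ends all non-pregnancy data collection, against the 30-day event rule and the post-discontinuation BMD follow-up, and pregnancy incidence (objective II.i) has no endpoint or rate analysis

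*Protocol*

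**What the plan says.** **Data collection.** Protocol section 11.2 sends every pregnancy into a dedicated process and states that "all other data collection will cease". Section 9.3.4 names pregnancy among the reasons for stopping Yselty permanently. For a patient who stops for any reason, section 11.3 says that "all events will be collected that occurred up to 30 days after the last administration". It also keeps patients with BMD decrease or osteoporosis in follow-up "unless they have completely withdrawn from the study", with bone-related AEs and all ADRs still collected. Section 9.2.6 says that these patients "should be observed in the study for up to 24 months after the last administration of" Yselty, and note 10 to Table 1 repeats that their BMD measurements are to be documented.

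**Objective II.i.** Section 8 words it as "To evaluate the incidence of adverse drug reactions (ADRs), serious adverse drug reactions (SADRs) and pregnancies (including pregnancy follow-up"). Under II.i, section 9.1.2 lists incidence rates of ADRs and of SADRs, section 9.3.6 lists ADRs and SADRs as variables, and section 9.7.3.4 analyses those two. Section 9.7.3.5 provides listings of special situations, which include pregnancy exposure.

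**Reporting limits.** The Special Situations part of section 11.1 counts use in pregnancy or breastfeeding as a special situation and says that those without an AE, or with a non-serious one, "are required to be reported within 7 calendar days". Section 11.4 says: "Drug exposure during pregnancy or lactation must be documented and forwarded to the MAH by the physician immediately (within 24 hours of awareness"). Section 11.2 applies the SAE limit to pregnancy and refers the reader to section 11.3 for it.

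**The concern.** The cease rule and the follow-up rules give opposite instructions for the same patient, and no section says which prevails. A site that applies 11.2 literally records no maternal AE or ADR in the 30 days after the last dose, apart from what the pregnancy process captures. Where the woman already has BMD decrease or osteoporosis, it also stops recording routine DXA results and bone events. Sites may resolve this differently, so that missing data depend on which section a site read. ADRs lost in this way are missing from the II.i incidence rates, and BMD results lost are missing from the post-discontinuation BMD description.

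The second problem is one of traceability. The study enrols women of reproductive age and makes pregnancy incidence part of a stated objective, yet it plans no rate for it. A listing has no denominator and cannot answer a question about incidence.

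**Working it through.** The protocol states no figure for this point and no sample-size arithmetic applies. The check is to set the rules side by side.

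**Step 1: does the same patient fall under both rules?** Yes. Pregnancy is a reason for permanent discontinuation (9.3.4), and 11.3 applies to discontinuation for any reason.

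**Step 2: what must be collected after she stops, other than pregnancy data?**

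| Patient who stops because of pregnancy | Under 11.2 | Under 11.3 and 9.2.6 |
|---|---|---|
| No BMD decrease or osteoporosis | nothing further | all events up to 30 days after the last dose; final visit at discontinuation |
| BMD decrease or osteoporosis during the study | nothing further | all events up to 30 days; BMD assessments and relevant concomitant medication for up to 24 months; bone-related AEs and all ADRs |

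**Step 3: is there an exception for pregnancy?** None is stated. Section 11.3 names only complete withdrawal as ending the continued BMD follow-up. Section 9.2.6 and note 10 to Table 1 do not mention pregnancy. Section 11.2 exempts neither the 30-day window nor the BMD follow-up.

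**Step 4: does the pregnancy process fill the gap?** Only in part. The items in 11.2 are prior pregnancies, expected delivery date, prenatal tests, outcome, information on the child, complications, and causality of an abnormal outcome. DXA results, fractures and general maternal AEs or ADRs are not among them.

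**Step 5: trace objective II.i through the protocol.**

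| Place | ADRs | SADRs | Pregnancies |
|---|---|---|---|
| Objective (section 8) | yes | yes | yes, with follow-up |
| Endpoint (9.1.2) | incidence rate | incidence rate | none |
| Variable (9.3.6) | yes | yes | none |
| Analysis (9.7.3.4) | incidence and EAIR, 95% CI | incidence and EAIR, 95% CI | none |
| Other output (9.7.3.5) | incidence and EAIR | incidence and EAIR | listing of special situations |

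**Step 6: compare the reporting limits.** For pregnancy exposure without a serious event, the general sentence in 11.1 gives 7 calendar days, while 11.2 and 11.4 give the SAE limit of 24 hours. The difference is 7 − 1 = 6 days. Section 11.1 refers to 11.2 for pregnancy, and the 7-day list in 11.4 leaves pregnancy out. The cross-reference from 11.2 to 11.3 is wrong, because 11.3 contains no time limit; the SAE limit is in 11.4.

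**The case against.** The best defence of the cease rule is that it is specific and overrides the general follow-up rules. That reading is possible, but the text does not establish it: 11.3 applies to any reason for stopping and names complete withdrawal as the only exception to the BMD follow-up.

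A second defence concerns the analysis of patients followed after stopping. Section 9.7.3.4 describes "patients who experienced BMD decrease during the study but continued to be observed in the study, regardless of the reason for which" treatment stopped. Because this subgroup is conditional on continued observation, a woman whose data collection ended is simply outside it. The defence stands: that paragraph imposes no duty to follow her and does not contradict 11.2. The conflict lies between 11.2 on one side and 9.2.6 and 11.3 on the other.

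On objective II.i, it can be said that 11.1 lists maternal exposure among what an AE may be, that 9.7.3.5 tabulates AEs with EAIRs, that 9.7.1 promises a descriptive analysis of all variables, and that the SAP may add detail. This softens the point, since some count could emerge. But 11.1 marks maternal exposure as a special situation, and 9.7.3.5 assigns special situations to listings. The protocol also sets out endpoints objective by objective and omits this component, which is a mismatch within the protocol and not a detail deferred to the SAP.

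On the reporting limits, the defence largely holds. The reference in 11.1 to 11.2, read with 11.4, points to one limit, and only the general sentence lacks an exception.

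**Conclusion.** The point holds as a conflict of instructions and an objective without an endpoint. For a participant who stops because of pregnancy, other data collection runs for 0 days under 11.2, against 30 days of events under 11.3. If she already had BMD decrease or osteoporosis, it is also 0 against up to 24 months of bone follow-up. The protocol gives no pregnancy rate, so the number of women cannot be stated.

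Three stronger readings are not supported:

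- A reader might infer that every pregnant participant loses 24 months of BMD data. Section 9.2.6 gives that follow-up only to patients with BMD decrease or osteoporosis; for all others the final visit is at discontinuation. DXA is also recorded only when done in routine care, so the amount of bone data lost cannot be derived.
- A reader might infer that pregnancy affects bone and so biases the recovery results. The protocol says nothing of this, and pregnancy is not among the bone risk factors in 9.2.1 or 9.3.2.
- A reader might infer harm to the primary endpoint. It is assessed in users treated for more than 12 months with available z-scores, and no effect on it is shown.

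The reporting limits are a minor wording matter.

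**What to change.** 1. Reconcile section 11.2 with sections 9.2.6 and 11.3, so that the protocol says explicitly whether 30-day event collection continues alongside pregnancy follow-up. It should say the same for the post-discontinuation documentation of routinely available BMD results and bone events. The documents do not show which rule was intended, so the sponsor must decide and use the same wording in each place, including note 10 to Table 1.
2. Under objective II.i, add to 9.1.2, 9.3.6 and 9.7.3.4 the number and exposure-adjusted incidence of pregnancies with 95% CI, and pregnancy outcomes by category. State which pregnancies count and over what time at risk.
3. As a minor correction, align the general 7-day sentence in section 11.1 with 11.2 and 11.4, and correct the reference in 11.2 so that it leads to the section containing the SAE limit (11.4).

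The cost is protocol wording and one table. The protocol already plans to collect pregnancies and their outcomes (11.2) and treatment start and stop dates (9.3.4). The pregnancy questionnaire belongs to the risk management plan, which is not shown, so its content could not be checked. The change is best made before data collection starts, planned for Q1/Q2 2026, because data not collected under the cease rule may not be recoverable at analysis.
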